Appendix A
Diabetes Quality of Life for Youths Questionnaire (DQOL)

A: **DIRECTIONS:** Read each statement carefully. Please indicate how satisfied or dissatisfied you currently are with the aspect of your life described in the question. Mark [X] the box that matches how satisfied or dissatisfied you feel: 1 = Very Satisfied, 2 = Moderately Satisfied, 3 = Neither Satisfied nor Dissatisfied, 4 = Moderately Dissatisfied, 5 = Very Dissatisfied. There are no right or wrong answers to these questions. We want your opinion.

	Very Satisfied [1]	Mod. Satisfied [2]	Neither [3]	Mod. Dissatisfied [4]	Very Dissatisfied [5]
A1: How satisfied are you with the amount of time it takes to manage your diabetes?					
A2: How satisfied are you with the amount of time you spend getting checkups?	[1]	[2]	[3]	[4]	[5]
A3: How satisfied are you with the time it takes to determine your blood sugar?	[1]	[2]	[3]	[4]	[5]
A4: How satisfied are you with your current medical treatment?	[1]	[2]	[3]	[4]	[5]
A5: How satisfied are you with the flexibility you have with your diet?	[1]	[2]	[3]	[4]	[5]
A6: How satisfied are you with the burden your diabetes is placing on your family?	[1]	[2]	[3]	[4]	[5]
A7: How satisfied are you with your knowledge about your diabetes?	[1]	[2]	[3]	[4]	[5]

SPEAKING GENERALLY:

		Very Satisfied	Mod. Satisfied	Neither Satisfied	Mod. Dissatisfied	Very Dissatisfied
A8:	How satisfied are you with your sleep?	[1]	[2]	[3]	[4]	[5]
A9:	How satisfied are you with your friendships?	[1]	[2]	[3]	[4]	[5]
A10:	How satisfied are you with your work, school, and household activities?	[1]	[2]	[3]	[4]	[5]
A11:	How satisfied are you with the appearance of your body?	[1]	[2]	[3]	[4]	[5]
A12:	How satisfied are you with the time you spend exercising?	[1]	[2]	[3]	[4]	[5]
A13:	How satisfied are you with your leisure time?	[1]	[2]	[3]	[4]	[5]
A14:	How satisfied are you with life in general?	[1]	[2]	[3]	[4]	[5]
A15:	How satisfied are you with performance in school?	[1]	[2]	[3]	[4]	[5]
A16:	How satisfied are you with how your classmates treat you?	[1]	[2]	[3]	[4]	[5]
A17:	How satisfied are you with your attendance at school?	[1]	[2]	[3]	[4]	[5]

Compared with others your age, would you say your health is:

- Excellent
- Good
- Fair
- Poor

DIRECTIONS: Read each statement carefully. Please indicate How Often the following events happen to you. Mark [X] the box that matches how satisfied or dissatisfied you feel: 1 = Never, 2 = Very Seldom, 3 = Sometimes, 4 = Very Often, 5 = All the time. There are no right or wrong answers to these questions. We are interested in your honest opinion.

Never Very Seldom Sometimes Often All the time

B1: How often do you feel pain [1] [2] [3] [4] [5]

associated with the treatment of
your diabetes?

B2: How often are you embarrassed [1] [2] [3] [4] [5]
by having to deal with your
diabetes in public?

B3: How often do you feel [1] [2] [3] [4] [5]
physically ill?

B4: How often does your diabetes [1] [2] [3] [4] [5]
interfere with your family life?

B5: How often do you have a bad [1] [2] [3] [4] [5]
night's sleep?

B6: How often do you find your [1] [2] [3] [4] [5]
diabetes limiting your social
relationships and friendships?

B7: How often do you feel good [1] [2] [3] [4] [5]
about yourself?

B8: How often do you feel
restricted by your diet? [1] [2] [3] [4] [5]

B9: How often does your diabetes
keep you from driving a car? [1] [2] [3] [4] [5]

B10: How often does your diabetes
interfere with your exercising? [1] [2] [3] [4] [5]

B11: How often do you miss work,
school or household duties
because of your diabetes? [1] [2] [3] [4] [5]

B12: How often do you find yourself
explaining what it means to
have diabetes? [1] [2] [3] [4] [5]

B13: How often do you find that your diabetes
interrupts your leisure time activities? [1] [2] [3] [4] [5]

B14: How often are you teased
because you have diabetes? [1] [2] [3] [4] [5]

B15: How often do you feel that
because of your diabetes you go
to the bathroom more than others? [1] [2] [3] [4] [5]

B16: How often do you find you eat
something you shouldn't rather
than tell someone that you have diabetes? [1] [2] [3] [4] [5]

B17: How often do you hide from
others the fact that you are
having an insulin reaction? [1] [2] [3] [4] [5]

B18: How often do you find that your diabetes prevents you from participating in school activities (for example, a school play, playing a sport). Never [1] Very Seldom [2] Sometimes [3] Often [4] All the time [5]

B19: How often do you find that your diabetes prevents you from going out to eat with your friends? [1] [2] [3] [4] [5]

B20: How often do you feel that your diabetes will limit what job you will have in the future? [1] [2] [3] [4] [5]

B21: How often do you find that your parents are too protective of you? [1] [2] [3] [4] [5]

B22: How often do you find that your parents worry too much about your diabetes [1] [2] [3] [4] [5]

B23: How often do you find that your parents act like diabetes is their disease, not yours? [1] [2] [3] [4] [5]

DIRECTIONS: Read each statement carefully. Please indicate how often the following events happen to you. Check [X] the appropriate box. There are no right or wrong answers to these questions. If the question is not relevant to you, check "Does not apply".

		Does Not Apply [0]	Never [1]	Seldom [2]	Sometimes [3]	Often [4]	All the Time [5]
C1:	How often do you worry about whether you will get married?						
C2:	How often do you worry about whether you will have children?	[0]	[1]	[2]	[3]	[4]	[5]
C3:	How often do you worry about whether you will not get a job you want?	[0]	[1]	[2]	[3]	[4]	[5]
C4:	How often do you worry about whether you will pass out?	[0]	[1]	[2]	[3]	[4]	[5]
C5:	How often do you worry about whether you will be able to complete your education?	[0]	[1]	[2]	[3]	[4]	[5]
C6:	How often do you worry that your body looks different because you have diabetes?	[0]	[1]	[2]	[3]	[4]	[5]
C7:	How often do you worry that you will get complications from your diabetes?	[0]	[1]	[2]	[3]	[4]	[5]
C8:	How often do you worry whether someone will not go out with you because you have diabetes?	[0]	[1]	[2]	[3]	[4]	[5]

		Does Not Apply	Never	Seldom	Sometimes	Often	All the Time
C9:	How often do you worry that teachers treat you differently because of your diabetes?	[0]	[1]	[2]	[3]	[4]	[5]
C10:	How often do you worry that your diabetes will interfere with things that you do in school (sports, music, drama)?	[0]	[1]	[2]	[3]	[4]	[5]
C11:	How often do you worry that your diabetes causes you to do things with friends like going on dates or going to parties?	[0]	[1]	[2]	[3]	[4]	[5]

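### The quality-of-life form in Appendix A has wording faults in section B and item C11 that should be corrected before launch, and the handling of its 0 code and of item B7 should be confirmed

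*Protocol*

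**What the plan says.** The Instruments section of the protocol gives the YDQOL as one of two questionnaires completed online at all three time points, and cites a Cronbach alpha of 0.92 from the published measure. Appendix A prints the form. It has 17 numbered items in section A, 23 in section B and 11 in section C, 51 in all.

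- **Section A** runs from best to worst: "1 = Very Satisfied, 2 = Moderately Satisfied, 3 = Neither Satisfied nor Dissatisfied, 4 = Moderately Dissatisfied, 5 = Very Dissatisfied".
- **Section B directions** first ask how often events happen, then instruct: "Mark [X] the box that matches how satisfied or dissatisfied you feel: 1 = Never, 2 = Very Seldom". The full key there is "1 = Never, 2 = Very Seldom, 3 = Sometimes, 4 = Very Often, 5 = All the time". The column head and the scale repeated at B18 label code 4 'Often'.
- **Item B7** begins "B7: How often do you feel good" and goes on to refer to the respondent's view of themselves. It carries the same 1 to 5 codes as the items around it.
- **Section C** is headed "Does Not Apply [0" (closing bracket cut), followed by 'Never' at 1 through 'All the Time' at 5. Its directions say "If the question is not relevant to you, check" and name that box.
- **Item C11** reads "How often do you worry that your diabetes causes you to do things with friends like going on dates or going to parties".

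Planned Analysis names a two-way repeated measures ANOVA. The protocol does not say how YDQOL items are combined, reversed or recoded.

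**The concern.** The form is what participants will see, so its wording decides what is measured. A respondent told to mark satisfaction on a scale of frequencies has two instructions that cannot both be followed. One code with two labels leaves the fourth step of the section B scale uncertain. C11, read literally, asks about worry that diabetes makes the respondent socialise, which is hard to place among items about worry. The alpha taken from the published measure supports this form only as far as the wording matches.

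The numeric codes raise a second, weaker question. If the online system stores the printed numbers and someone adds them, a mark of irrelevance would count as better than never worrying, and B7 would pull against the rest of section B. Participants are aged 12 to 17, and the items on marriage, children, jobs and dating may well be marked not applicable by some of them.

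**Working it through.** The protocol gives no YDQOL score, range or scoring rule, so there is no figure of its own to reproduce. The check has two parts.

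**1. Wording, set side by side**

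| Place | One statement | The other |
|---|---|---|
| Section B task | Directions, opening: how often events happen. All 23 items also start with 'How often' | Directions, next instruction: mark how satisfied or dissatisfied one feels |
| Section B, code 4 | Directions: 'Very Often' | Column head and B18: 'Often' |
| C10 and C11 | C10: worry that diabetes will interfere with school activities | C11: worry that diabetes brings about activities with friends |

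The satisfaction phrase in section B also appears in the section A directions, where it fits. The 'Often' label occurs twice and 'Very Often' once.

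**2. What the printed codes would do if summed literally**

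Inputs, from Appendix A: A = 17, B = 23 and C = 11 items; codes 1 to 5, plus 0 in section C.

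- *Range.* With every item answered 1 to 5, the total runs from 51 to 5 × 51 = 255. With 0 counted as a value in section C, the minimum is 17 + 23 + 0 = 40.
- *Per item.* 'Does Not Apply' minus 'Never' = 0 − 1 = −1 point. Over section C this reaches 11 × (−1) = −11: all 'Does Not Apply' sums to 0, all 'Never' to 11.
- *Worked case.* Three items not applicable and code 2 on the other eight: literal sum = 8 × 2 + 3 × 0 = 16. Prorated sum = 11 × (16/8) = 22.
- *B7.* If x is the answer, the reversed score is 6 − x and the error from not reversing is x − (6 − x) = 2x − 6. For x = 1 to 5 this is −4, −2, 0, +2, +4.
- *Effect of B7 on a change.* Suppose every section B item improves by the same amount d. The correct change in the sum is −23d. With B7 unreversed it is −22d + d = −21d, so 21/23 = 91% is kept. Over all 51 items the share kept is 49/51 = 96%.

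How often 'Does Not Apply' will be used is not given in the protocol, so the arithmetic bounds the effect on one respondent and does not estimate the effect on the trial.

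**The case against.** The best answer is that most of this is harmless. The section B directions open with the right task, every item asks how often, and every anchor is a frequency, so most respondents will understand what is wanted. Both arms complete the same form. C11 is one item of 51, and whether its wording departs from the source cannot be settled without that source. This limits the size of the wording faults. It does not remove them: they are in the current text, and no analysis step can recover what a respondent meant.

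On the codes the objection is stronger. A reader might infer from the printed numbers that quality-of-life scores will be wrong. The documents do not support that. A 0 box with an explicit instruction for irrelevant questions works as a response code, and keeping it distinct lets an analyst exclude it. A positively worded item is an ordinary questionnaire feature. Excluding 0 and reversing B7 are rules that commonly sit in a scoring manual or statistical analysis plan. Neither is shown, so their absence from the protocol is no finding.

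A reader might also infer a material loss of power. For section C alone, a simulation with a standardised effect of 0.5, 43 per arm, baseline adjustment, 20% of answers 'Does Not Apply' and 30% of items re-marked between visits gave power of 57% with 0 coding against 67% with the mean of applicable items. All of these except the arm size are assumptions, and the analysis is not the planned repeated measures ANOVA. Section C is 11 of 51 items. A similar simulation of the 51-item total showed a loss of about one percentage point or less. The section C figures therefore say nothing about quality of life overall. The idea that the course changes which items adolescents call inapplicable has no basis in the documents.

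**Conclusion.** The wording faults stand on the text alone: the satisfaction instruction in section B, the two labels for code 4, and the odd sense of C11. That C11 has lost a negation is a plausible reading that the protocol cannot confirm. No numerical effect can be attached to these faults.

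The 0 code and B7 are risks that depend on one condition, that printed codes are summed as they stand, which the protocol nowhere says will happen. Under that condition a respondent's section C score could be up to 11 points too favourable relative to 'Never', and B7 would cost 2/23 of a uniform section B change or 2/51 of a uniform total change. The severity is minor.

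**What to change.** Before the online form goes live:

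1. Reword the section B directions so that they ask only for frequency.
2. Use one label for code 4 throughout section B.
3. Check C11 against the cited source instrument and restore the source wording if it differs.

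As a secondary safeguard, confirm in the scoring rules that 'Does Not Apply' is stored as not applicable and never as a score of 0. If section C is prorated, set a minimum number of answered items, because a respondent who marks all 11 as not applicable has no prorated score. Confirm also that B7 is scored as 6 minus the answer.

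The cost is two text corrections, one check against the source and two scoring lines, on a website that the MBSR Online Intervention section describes as still being built. After Time 1 data have been collected, rewording would leave visits that are no longer comparable.

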Appendix B

Mindful Attention Awareness Scale - Adolescent (MAAS-A)

Instructions: Below is a collection of statements about your everyday experience. Using the 1-6 scale below, please indicate how frequently or infrequently you currently have each experience. Please answer according to what really reflects your experience rather than what you think your experience should be. Please treat each item separately from every other item.

1 Almost Always	2 Very Frequently	3 Somewhat Frequently	4 Somewhat Infrequently	5 Very Infrequently	6 Almost Never
I could be experiencing some emotion and not be conscious of it until some time later.				1 2 3 4 5 6	
I break or spill things because of carelessness, not paying attention, or thinking of something else.				1 2 3 4 5 6	
I find it difficult to stay focused on what's happening in the present.				1 2 3 4 5 6	
I tend to walk quickly to get where I'm going without paying attention to what I experience along the way.				1 2 3 4 5 6	
I tend not to notice feelings of physical tension or discomfort until they really grab my attention.				1 2 3 4 5 6	
I forget a person's name almost as soon as I've been told it for the first time.				1 2 3 4 5 6	
It seems I am "running on automatic," without much awareness of what I'm doing.				1 2 3 4 5 6	
I rush through activities without being really attentive to them.				1 2 3 4 5 6	
I get so focused on the goal I want to achieve that I lose touch with what I'm doing.				1 2 3 4 5 6	
I find myself listening to someone with one ear, doing something else at the same time.				1 2 3 4 5 6	
I drive places on "automatic pilot" and then wonder why I went there.				1 2 3 4 5 6	
I find myself preoccupied with the future or the past.				1 2 3 4 5 6	
I find myself doing things without paying attention.				1 2 3 4 5 6	
I snack without being aware that I'm eating				1 2 3 4 5 6	

Appendix C
Demographic Data Sheet (DDS)

DIRECTIONS: Please complete the following information.

1. Age: _____
2. Date of Birth: _____ / _____ / _____
3. Gender
 Male
 Female
4. Race and/or Ethnic Origin, may check more than one:
 Caucasian
 African American
 Hispanic
 Asian
 Native American/Eskimo
 Other, Please specify
5. School Grade: _____
6. Level of Activity:
 Sedentary (very little physical activity)
 Moderately Active
 Very Active
7. How many year with diabetes? _____
8. Do you have a parent(s) with diabetes?
 Yes
 No
9. Do you have a sibling(s) with diabetes?
 Yes
 No
10. Do you wear an insulin pump?
 Yes
 No
11. Do you wear a continuous glucose meter?
 Yes
 No

Appendix D
HbA_{1c} Values Associated with Average Blood Glucose Values

HbA_{1c} (%)	eAG (estimated average glucose)		
	(mmol/mol)^[25]	(mmol/L)	(mg/dL)
5	31	5.4 (4.2–6.7)	97 (76–120)
6	42	7.0 (5.5–8.5)	126 (100–152)
7	53	8.6 (6.8–10.3)	154 (123–185)
8	64	10.2 (8.1–12.1)	183 (147–217)
9	75	11.8 (9.4–13.9)	212 (170–249)
10	86	13.4 (10.7–15.7)	240 (193–282)
11	97	14.9 (12.0–17.5)	269 (217–314)
12	108	16.5 (13.3–19.3)	298 (240–347)
13	119	18.1 (15–21)	326 (260–380)
14	130	19.7 (16–23)	355 (290–410)
15	140	21.3 (17–25)	384 (310–440)
16	151	22.9 (19–26)	413 (330–480)
17	162	24.5 (20–28)	441 (460–510)
18	173	26.1 (21–30)	470 (380–540)
19	184	27.7 (23–32)	499 (410–570)

Appendix E

Reminder Text/email content:

Hello,

This is a reminder that the HbA1c test kit has been sent. Please take 5 minutes to obtain and email these results. Thank you.

Please email or text with any questions.

Thanks,

[name]

[contact] cell

Appendix F

Flier to be posted in the Pediatric Endocrinology offices and at Diabetes Camps

Invitation to Participate in a Research Study

Adolescents ages 12-17 with Type 1 Diabetes

This study will examine the effects of
Mindfulness Based Stress Reduction (MBSR)

This Mindfulness program may help positive youth development and resilience by teaching core mindfulness practices. Participants learn valuable strategies to focus on the present and stop worrying about the past or future.

The research is done via an online, age-appropriate website. Participants will be required to have access to a computer and the Internet. Participants will receive a \$15 *iTunes* or *Amazon* gift card for completing the first part of the study and then an additional \$25 *iTunes* or *Amazon* gift card at the end of the study.

For additional information please contact:
[name], MSN, RN, PhD candidate
Duquesne University School of Nursing
[contact]
[contact]

Appendix G

Sample Pediatric Endocrinologist Recruitment Letter

April 1, 2015

[name]
Pediatric Endocrinology

Dear [name],

This letter is to request the participation of your office in research concerning the use of Mindfulness as a stress management technique for adolescents with Type 1 diabetes.

I am conducting this study as partial fulfillment of the requirements for the PhD degree in Nursing at Duquesne University. IRB approval to conduct this study has been obtained through Duquesne University.

I am asking for your help to recruit adolescents between the ages of 12 to 17 with Type 1 diabetes to participate in this study. Participants will be randomized to the experimental group or the waitlist/control group. If interested, the participants will be invited to learn the practice of mindfulness via modules on a website, asked to practice the MBSR techniques, and asked to respond to questionnaires via a secure online data collection site. The home page of the website where your patient will access the course material is www.mysweetmind.org.

If you agree to help me recruit, business cards and postcards will be provided to you to give to your patients and their parents that will contain information about the study. If your patients are interested, they will be asked to contact me directly. Participants would be under no obligation to join the study or continue in the study once they join.

Please complete and send via U.S. Mail the enclosed pre-stamped postcard if you permit this study to be advertised in your office. I am available to meet with you and/or your staff directly to describe the study further or answer any questions you may have.

I encourage you to consider this opportunity for your patients. Mindfulness has become quite popular in the last few years and has shown significant benefits for many different individuals with varying conditions/illnesses. The skills that your patient could gain have the potential for helping them for a lifetime.

Please do not hesitate to contact me with any questions. My cell phone number is [contact]

Sincerely,

[name], MSN, RN, CNE
PhD Candidate
Duquesne University
School of Nursing

Appendix H

Return Post Card

Yes, I am interested in advertising this study in our Pediatric Endocrinology office

Please send a packet of information with post card/business cards to my office.

Name: _____

Group Name: _____

Address: _____

Please check here if you would like an office visit by the investigator _____

Please check here if you would like to discuss the study via telephone with the researcher _____

Please check here if you would like additional information sent via e-mail _____

Best time/method to contact you _____

Appendix I

Key Concepts for www.mysweetmind.org Module Content

Module 1 – Introduction to Mindfulness and Mindful Eating

Key Concepts

Sometimes when you experience a lot of stress, you get stuck in your thoughts and spend a lot of time feeling bad about the past or worrying about the future. This can cause you to feel bad and maybe act badly toward yourself or toward others.

This is why learning how to handle stress is so important

Mindfulness is defined by [name] as “Paying attention in a particular way: on purpose, in the present moment, and nonjudgmentally” (1994, 4).

Mindfulness is about learning to handle stressful situations with kindness and compassion toward yourself. Learning how to be mindful will help you to be more resilient – which means you are able to thrive and do well despite stressful situations. These modules, starting with this one, will give you information about specific mindfulness practices and access to audio recordings to listen to.

Your body and your brain are constantly sending signals back and forth, they are in communication constantly.

Explain the Hand Model of the Brain – the lizard brain

Explain Paper Tigers – knowing the difference

Breathing is the Heart of Mindfulness – recorded track

Pay careful attention to your breath, you don’t need to change your pattern of breathing – just bring your attention to your natural breath. You may want to focus in on that part of your body where you notice the breath the most – your nose, your belly, your lungs.

Eating a Raisin Mindfully - recorded track

Module 2 – Sitting Meditation

Key Concepts

Mindfulness is sometimes described as a bird with two wings: compassion and awareness. In order to practice Mindfulness – like flight – you need both wings.

Awareness will help you recognize that you are feeling stressed.

Compassion will allow you to look at your situation with kindness – smiling will help you to cultivate this self-compassion and compassion toward others. Be aware if you are being negative or self-critical and if this is happening to you simply be aware of it and then meet those thought with kindness so they will let go of you.

Mindfulness of the breath is the foundation of every one of the mindfulness practices – simply being aware of the breath is a powerful antidote to stress. Breath and smile.

Just Sit and do nothing. Shift out of autopilot and switch from “doing” to “being” Just sit and be aware of the breath.

Sitting like a Mountain. – recorded track

Daily practice is important

Module 3 – Body Scan

Key Concepts

Don’t allow yourself to be pulled away from the present moment, recognize the healing power of a simple present-moment experience.

If you notice yourself thinking about the past or the future or realize your mind has wondered, simply return to the present by using your breathing as an anchor.

Mindfulness will help you to notice the good things that happen in life more because you will be more aware of and grateful for the positive things in your life by spending some time in the present moment considering those things you are grateful for....

Since the mind and the body are deeply connected, releasing stress in your body will help you to release stress in your mind. This is what the body scan allows you to do. It is a gift to your body because it is an invitation of energy into the body from your mindfulness practice.

The body scan is good to practice at night before you go to sleep also.

Body Scan – recorded track

Handling Pain and Discomfort with the Body Scan

Module 4 – Mindfulness of Thinking and Everyday Mindfulness

Key Concepts

Too busy for mindfulness? Stories of including mindfulness in everyday living

Informal Mindfulness – bringing mindful awareness into routine activities you already have

Mindful Eating

The link between formal and informal mindfulness practice – SOBER

1. Stop
2. Observe
3. Breathe
4. Expand
5. Respond

Practice mindfulness in small ways everyday

Module 5 – Loving Kindness Meditation & Mindfulness Movement

Key Concepts

Loving Kindness Meditation

Your thoughts are powerful and can become your reality

Automatic thoughts exercise.

Mindfulness of thinking – recorded track

Mindful movement is the practice of moving your body intentionally with care and attention to what is happening with each movement.

Mindful movement – recorded track

Module 6 – Review & Tips for Maintaining Mindfulness Practice

Key Concepts

Breath

Awareness and Compassion

Listen to recordings

Mindfulness in a Moment and in Everyday Living

References

Bernstein, C. M., Stockwell, M. S., Gallagher, M. P., Rosenthal, S. L., & Soren, K. (2013). Mental health issues in adolescents and young adults with type 1 diabetes: Prevalence and impact on glycemic control. *Clinical Pediatrics*, 52(1), 10-15. doi:10.1177/0009922812459950

